12.5.3 Analysis of the Secondary Endpoints

If both the mid- and top-doses are shown to be statistically significantly better than placebo for the primary endpoint using the Fisher's LSD procedure, then the secondary endpoints will be tested in a stepwise way to preserve the familywise type 1 errors. Details of the stepwise testing procedure for secondary efficacy endpoints will be described in a prospective SAP.

Percent of subjects achieving a reduction $\geq 5\%$ from baseline in BMI at Week 56 will be analyzed using a logistic regression, with treatment, age and gender stratification as the main effect and baseline BMI value as a covariate at the 0.05 significance level. The adjusted odds ratios between the top-dose and placebo and between the mid-dose and placebo will be calculated together with their 95% confidence intervals. The p-values for the comparisons will also be generated.

The percent of subjects achieving a reduction $\geq 10\%$ and $\geq 15\%$ from baseline in BMI at Week 56 will be analyzed similarly.

Secondary efficacy endpoints that are continuous variables will be analyzed by a similar MMRM model as for the primary endpoint where the baseline BMI value will be replaced by the baseline value of the corresponding endpoint as a covariate.

The above analyses will be conducted for both the ITT and m-ITT populations.

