## 6. Statistical Methods

### 6.1 General Principles

All data processing, summarization and analyses will be performed using SAS Environment / Version 9.3 (or later) of the SAS® statistical software package.

The following principles will be applied to all TFLs unless otherwise stated:

Principle	Value
Significant tests	Two-sided and use a 5% significance level.
Treatment group labels and order presented	Placebo VI-0521 Mid VI-0521 Top
Tables	Data in summary tables presented by treatment group, assessment and visit (where applicable).
Listings	All data collected presented by treatment group, site, subject, and visit (where applicable), unless otherwise specified.
Descriptive summary statistics for continuous variables	Number of observations (N), mean, standard deviation (SD), minimum, median and maximum.
Descriptive summary statistics for categorical variables	Frequency counts and percentages [n (%)].
Denominator for percentages	Number of subjects in the pertinent analysis population, unless stated otherwise in table shells.
Include "Missing" as category	Demographics and Other Baseline Characteristics only
Display for 0 percentages	Blank
Display to one more decimal place than collected value	Mean Median Minimum Maximum
Display to two more decimal places than collected value	Standard Deviation Confidence Interval
Limit of precision for displays	3 decimal places
Date Format	DDMMYYYY

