### 6.6.2 Secondary Efficacy Analysis

If both the mid- and top-dose are shown to be statistically significantly better than placebo for the primary endpoint using the Fisher's LSD procedure, then the secondary endpoints will be tested in a stepwise way to preserve the familywise type 1 errors.

Starting from top-dose of VI-0521 treatment, hypothesis tests for secondary efficacy endpoints will be based on null hypotheses that assume no *a priori* differences between placebo and top-dose treatment.

A closed or sequential testing procedure will be used for testing the key secondary efficacy variables. With this hierarchical procedure, the key secondary efficacy variables will only be tested if the primary efficacy analysis is statistically significant.

Analyses will be carried out for the key secondary variables.

Within the key secondary variables, the statistical significance level will be adjusted using the Hochberg method, controlling the familywise error rate at 5%. Correlation

analysis will be implemented among the key secondary variables to ensure the conditions required for Hochberg procedure are satisfied. All endpoints have to be statistically significant in favor of top-dose VI-0521 treatment compared to placebo, after the Hochberg adjustment, in order for the next set in the hierarchy to be tested. The testing is only stopped when all of the alpha is 'exhausted'. The sequential testing will stop at the first endpoint set where top-dose VI-0521 treatment does not demonstrate statistical superiority over placebo.

The above process will be repeated on mid-dose of VI-0521 treatment.

Percent of subjects achieving a reduction  $\geq 5\%$  from baseline in BMI at Week 56 will be analyzed using a logistic regression, with treatment, age and gender stratification as the main effect and baseline BMI value as a covariate at the 0.05 significance level. The adjusted odds ratios between the top-dose and placebo, between the mid-dose and placebo, and between the top-dose and mid-dose will be calculated together with their 95% confidence intervals. The p-values for the comparisons will also be generated.

The percent of subjects achieving a reduction  $\geq 10\%$  and  $\geq 15\%$  from baseline in BMI at Week 56 will be analyzed similarly.

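### SAP 6.6.2 claims 5% familywise control for key secondary variables tested in ordered sets, but names neither variables, sets nor order and gives no rule for alpha between doses, so the 5% is not guaranteed

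*SAP*

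**What the plan says.** Protocol 12.5.3 opens secondary testing only if both doses beat placebo on the primary endpoint, and leaves the rest to the SAP: "Details of the stepwise testing procedure for secondary efficacy endpoints will be described in a prospective SAP".

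SAP 6.6.2 is where that detail should be. It says:

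- "A closed or sequential testing procedure will be used for testing the key secondary efficacy variables".
- "Analyses will be carried out for the key secondary variables".
- Among the key variables, "the statistical significance level will be adjusted using the Hochberg method, controlling the familywise error rate at 5" percent.
- Every endpoint in a set must favour the top-dose after adjustment "in order for the next set in the hierarchy to be tested".
- "The sequential testing will stop at the first endpoint set where top-dose VI-0521 treatment does not demonstrate statistical superiority over placebo". The sentence just before this one says instead that testing ends only once all alpha is 'exhausted'.
- "The above process will be repeated on mid-dose of VI-0521 treatment".

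SAP 3.2 and Protocol 6.2 list the secondary endpoints as plain bullets. No bullet is marked key, none is assigned to a set, and neither section says that the printed order is the test order. SAP 7 records no changes to the planned analysis. The general rule in SAP 6.1 for tests is "Two-sided and use a 5% significance level".

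**The concern.** A gated procedure with Hochberg inside each set controls the familywise error only if the sets and their order are fixed independently of the unblinded data. Here the rule cannot be run until someone decides which endpoints are key, how they are grouped and which group comes first. If that decision came after the treatment codes were known, it would determine which endpoints are declared significant, and the 5% would no longer describe the procedure.

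The mid-dose repeat is a second gap. Without an alpha rule, the natural reading is a fresh 5% for each dose, and that spends more than 5% on the secondary claims as a whole.

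At stake are the formal claims on responder rates, waist, insulin sensitivity, lipids and blood pressure. The primary analysis is not affected.

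**Working it through.** **Inputs from the documents.** Level 5%, two-sided (SAP 6.1, 6.6.2). Allocation 50 placebo, 50 mid-dose, 100 top-dose (SAP 2.3). Candidate endpoints per dose (SAP 3.2, with systolic and diastolic pressure separated as in 6.6.2): 3 responder cut-offs + 1 waist + 2 (insulin, Matsuda) + 2 (triglycerides, HDL-C) + 2 blood pressures = 10.

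**Assumptions.** The correlation between endpoints is not given; equal correlation of 0 to 0.8 is assumed. No endpoint has a true effect. Test statistics are normal. Both primary gates have been passed.

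**Hochberg rule.** With ordered p-values p(1) ≤ … ≤ p(m), at least one endpoint is declared significant if some p(j) ≤ 0.05/(m − j + 1). The whole set passes if p(m) ≤ 0.05.

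**Step 1: the plan's own 5%.** It cannot be reproduced, because the sets are not given. With sets supplied in advance, the error for the top-dose alone was (simulation, 200,000 runs):

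| Correlation | 0 | 0.3 | 0.5 | 0.8 |
|---|---|---|---|---|
| 3 responder endpoints, then the other 7 | 5.0% | 4.8% | 4.6% | 3.8% |
| All 10 in one set | 4.9% | 4.6% | 3.9% | 2.3% |

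The method therefore delivers 5% within a dose once its contents are fixed.

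**Step 2: first set chosen after seeing the p-values (top-dose, 10 candidates).**

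| Correlation | 0 | 0.3 | 0.5 | 0.8 |
|---|---|---|---|---|
| Best single endpoint | 40.1% | 35.0% | 28.7% | 17.1% |
| Best three, Hochberg | 16.1% | 14.5% | 12.5% | 8.5% |
| Best five, Hochberg | 9.6% | 8.7% | 7.5% | 5.2% |

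Check at zero correlation, single best: 1 − 0.95^10 = 1 − 0.5987 = 0.4013.

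**Step 3: sets fixed in advance, but each dose run at a full 5%.** Two independent families would give 1 − 0.95² = 9.75%. The doses share the placebo arm, so their contrasts have correlation (1/50)/√[(1/50 + 1/100)(1/50 + 1/50)] = 0.02/√(0.03 × 0.04) = 0.58, and the total is somewhat lower:

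| Correlation between endpoints | 0 | 0.3 | 0.5 | 0.8 |
|---|---|---|---|---|
| One Hochberg set of 10 per dose | 9.2% | 8.4% | 7.1% | 4.2% |

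Five sets following the bullets of SAP 3.2 give about 8-9% for correlation 0.5 to 0.

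**The case against.** **No selection is shown.** A reader might infer that the sets were chosen after unblinding, or that familywise control has failed. The documents support neither. Protocol 12.1 requires the SAP to be signed before the database is final, and Protocol 8.2 keeps the sponsor blinded. This stands: the figures in Step 2 are conditional, and the right conclusion is that 5% is not guaranteed.

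**The largest figures are near the worst case.** This also stands, for four reasons:

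- The 29-35% requires a first set of one hand-picked endpoint. Larger first sets bring Hochberg into play and lower the error.
- It counts significance in either direction, whereas SAP 6.6.2 requires results in favour of the drug. Counting favourable results only, the single best gives about 14-18% and the best three about 6-7% (correlation 0.5-0.3). The benchmark then also halves, to 2.5%.
- Three of the ten endpoints are cut-offs of the primary variable, so they are unlikely to be null once the primary gates are passed. With only the other seven null, the single-best figure is 23-27%, either direction.
- The three responder cut-offs are nested, so equal correlation of 0.3-0.5 describes them poorly. At 0.8 the inflation is smaller.

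**All ten endpoints could be one Hochberg family.** The Hochberg sentence alone allows this, and it would need no order and keep 5% within a dose. But the text then speaks of a next set and a first set, which one family does not have. It also leaves the mid-dose repeat unresolved.

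**The dose order is stated.** Top-dose comes first. That orders the doses, not the endpoints. Nor does it say whether mid-dose testing depends on the top-dose result.

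**Conclusion.** The omission is confirmed across both documents: no key variables, no sets, no order, and no alpha rule between doses. The 5% familywise control claimed for the secondary endpoints is not guaranteed by the procedure as written.

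- **If the first set were chosen on unblinded data:** about 12-15% per dose for the best three endpoints with Hochberg, and 29-35% for the single best. This assumes ten null endpoints, two-sided tests and correlation 0.5-0.3. Both are upper-end figures.
- **If sets are fixed in advance but each dose gets 5%:** about 7-9% across doses for correlation 0.5 to 0, with both primary gates passed and no secondary effects. With one set of ten at correlation 0.8 it is 4.2%, within 5%.

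The second result needs no misconduct or post hoc choice; it follows from reading the mid-dose repeat at face value. The SAP should be amended on this point.

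**What to change.** Before unblinding, amend SAP 6.6.2 as follows:

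1. **One table** naming the key variables, the set each belongs to and the order of the sets. The printed order of SAP 3.2 is a ready default: responders; waist; fasting insulin and Matsuda; triglycerides and HDL-C; blood pressures. The sponsor may choose another. Under the all-must-pass gate, a failed 15% responder test in set 1 would block every later set, so the grouping deserves thought.
2. **One alpha path across doses.** For example, test mid-dose sets only after all top-dose sets pass; with no secondary effects, any mid-dose error then follows a top-dose error already counted, so the total stays at the top-dose level of at most about 5%. Alternatively, split alpha, for example 2.5% + 2.5% = 5%.
3. **One stopping rule.** Keep either the stop at the first failed set or the rule about exhausted alpha, not both. In the same edit, choose between closed and sequential testing, and say what replaces Hochberg if the planned correlation check fails.

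The drafting cost is one table and a few sentences. The statistical cost is that fewer secondary results may be declared significant, most of all for the mid-dose if it waits on the top-dose.

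### The secondary testing procedure claims 5% familywise control, but its stop statements do not form one rule and its repeat for the mid-dose is not tied to the top-dose result

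*SAP*

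**What the plan says.** Protocol 12.5.3 leaves the stepwise procedure for the secondary endpoints to the SAP, so SAP 6.6.2 is the only place where it is fixed. That section provides as follows.

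- **Level.** Hochberg is applied within the key secondary variables, "controlling the familywise error rate at 5"%. SAP 6.1 makes all tests "Two-sided and use a 5% significance level".
- **Dependence check.** A correlation analysis among the key secondary variables is to be done "to ensure the conditions required for Hochberg procedure are satisfied". No criterion, data source, timing or consequence of a failed check is given.
- **Stop statement A.** "All endpoints have to be statistically significant in favor of top-dose VI-0521 treatment compared to placebo, after the Hochberg adjustment"; only then does testing move to the following set.
- **Stop statement B**, the next sentence. "The testing is only stopped when all of the alpha is" exhausted.
- **Stop statement C.** "The sequential testing will stop at the first endpoint set where top-dose VI-0521 treatment does not demonstrate statistical superiority over placebo".
- **Mid-dose.** The whole process is then repeated for the mid-dose. Neither an alpha split nor a condition on the top-dose result is stated.

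The key variables are not named and the sets are not listed. SAP 3.2 gives five secondary bullets. Counting each BMI threshold, each analyte, and systolic and diastolic pressure separately, they make 3 + 1 + 2 + 2 + 2 = 10 tests per dose.

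**The concern.** Suppose some but not all endpoints in a set are significant. Statement A stops. Statement B, taken literally, goes on, because the rejected endpoints have left alpha unspent. Statement C does not say whether superiority means every endpoint in the set or any of them, so it does not settle the matter by itself. With ten tests per dose a partly won set is a realistic outcome, and which later endpoints may be claimed as error-controlled would depend on the sentence followed.

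Two further features of the paragraph bear on the 5%. Hochberg's condition concerns the joint distribution of the test statistics. A sample correlation matrix of the variables cannot guarantee it, and the SAP does not say what follows from the result. Also, repeating the process for a second dose at the same level adds a second chance of a false claim unless the two doses are linked.

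**Working it through.** **Inputs.** Two-sided 5% tests (SAP 6.1). Hochberg at 5% (SAP 6.6.2). Allocation of 50 placebo, 50 mid-dose and 100 top-dose (SAP 2.3). The number and content of sets, the effect sizes and the correlations between endpoints are assumptions.

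**1. The plan's own 5%.** For two independent true nulls, Hochberg errs if both p-values are at most 0.05, or if exactly one is at most 0.025 and the other exceeds 0.05:

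0.05² + 2 × 0.025 × 0.95 = 0.0025 + 0.0475 = 0.0500.

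The stated figure reproduces for one Hochberg family in one dose.

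**2. Strict rule (A, with C read the same way).** Take the first set in the order that holds a true null. No type I error is possible before it. To go past it, every endpoint in it must be rejected, including the true null, so an error has already been made. The familywise error is therefore the chance of an error in that one set: 5.0% when the other endpoints are clearly effective. In simulation, with the five bullets as sets and one large effect in each, it was 4.7% to 5.0% for correlations of 0 to 0.6.

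**3. Going on at full alpha after a partly won set (one reading of B).** When the other endpoints in a set have p-values near zero, the true null has the largest p-value, and Hochberg compares that with the full 0.05. With one true null in each of k independent sets, the error is 1 − 0.95^k.

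| Case | Familywise error, one dose |
|---|---|
| Two sets, independent | 1 − 0.95² = 9.75% |
| Two sets, correlation 0.5 between the null statistics | 9.1% |
| Three sets, independent | 1 − 0.95³ = 14.3% |
| Five bullets as sets, one large effect in each, correlation 0 to 0.6 (simulated) | 18.4% down to 14.0% |

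In the last row the waist set has one endpoint, which is the effective one, so four sets hold true nulls. The independence value is 1 − 0.95⁴ = 18.5%.

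**4. The correlation condition.** Simulated Hochberg error with all nulls true, two-sided, equal correlation r:

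| Endpoints | Most negative r | r = 0 | r = 0.6 | r = 0.9 |
|---|---|---|---|---|
| 2 | 5.0% (r = −1) | 5.0% | 4.7% | 4.2% |
| 3 | 4.5% (r = −0.5) | 4.9% | 4.4% | 3.5% |
| 10 | 4.8% (r = −0.11) | 4.9% | 3.5% | 1.9% |

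No case exceeds 5% beyond simulation error. The general bound under arbitrary dependence, 0.05 × Σ(1/j), is 7.5% for 2 endpoints, 9.2% for 3 and 14.6% for 10. It is a bound, and nothing simulated came near it.

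**5. Two doses, each at a full 5%, no gate.** The two contrasts share the placebo arm:

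rho = (1/50) / √[(1/50 + 1/50)(1/50 + 1/100)] = 0.02 / √(0.04 × 0.03) = 0.577.

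For one endpoint that is null at both doses, the chance that at least one |Z| exceeds 1.96 is 8.8% (9.75% if the contrasts were independent). With the strict rule in each dose and the five bullets as sets, the simulated error over both doses was 7.8% to 9.0%. When the mid-dose was tested only after every top-dose set had been won, it was 4.4% to 5.0%.

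**The case against.** The strict rule is the better-supported reading. Statements A and C both point to it, and B can be made to fit: a set not won in full passes nothing on, so its alpha is exhausted. No sentence says that testing resumes at an undiminished 5% after a partial failure, and a procedure that passed on only unspent alpha need not inflate the error. The 9.75% and 14.3% therefore belong to a reading the SAP does not state, with sets it does not define. All of this stands. It narrows the point without removing it, because B as worded names exhaustion of alpha as the only ground for stopping and the SAP never defines the term.

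On the correlation check, a reader might infer more than the documents support in two respects.

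- **Opposite directions of effect.** Fasting insulin and the Matsuda index, or triglycerides and HDL-C, would be expected to correlate negatively, and that might seem to break Hochberg. It does not follow. The tests are two-sided, so reversing the scoring of an endpoint leaves its p-value unchanged, and the negative correlations simulated gave no inflation.
- **Choosing the method after unblinding.** The SAP names no data source or timing, a pooled correlation can be computed blind, and Hochberg is the only adjustment named. Data-driven selection is not in the text.

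What is left of the check is a step that cannot ensure what it is meant to ensure and that leads nowhere.

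**Conclusion.** The point holds as a defect of prespecification. The 5% claimed in SAP 6.6.2 follows from one reading of its stop statements and not from another, and the section does not say which governs. Per dose, the choice is between 5.0% and, if testing went on at full alpha, 9.75% for two independent sets (9.1% at correlation 0.5) or 14.3% for three. Those larger figures assume the sets, one true null in each, clear effects elsewhere, and a full-alpha continuation.

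The mid-dose repeat is a separate gap that remains under the strict rule. If it is run without a gate or alpha split, which the SAP leaves open, the error over both doses is about 8.8% for one endpoint at contrast correlation 0.577.

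It would go too far to say that the trial's secondary error rate exceeds 5%, or that Hochberg is invalid for these endpoints; neither is shown. The primary analysis is not affected.

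**What to change.** Amend SAP 6.6.2 before unblinding:

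1. Delete the sentence on exhausted alpha. Keep the rule that every endpoint in a set must be significant before the next set is tested, and word the last stop sentence to match.
2. Drop the correlation check. Either justify Hochberg in advance or name Holm, which needs no dependence condition, as the prespecified method.
3. Name the key secondary endpoints and list the sets in order.
4. State how the doses are linked: test the mid-dose only after all top-dose sets are won, or split alpha between the doses.

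Items 1 and 3 cost only wording. Under item 2, Holm loses a little power against Hochberg within a set; keeping Hochberg with a stated justification avoids that. Item 4 has a real price, since a gate can leave mid-dose endpoints untested and a split lowers the level for both doses, but without one of them the 5% cannot be claimed over both doses.

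### The ≥15% (and ≥10%) BMI responder models have no rule for zero placebo responders; the odds ratio would then be infinite and a Wald p-value, if that is the test used, uninformative.

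*SAP*

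**What the plan says.** For the ≥5% endpoint, SAP 6.6.2 states that it "will be analyzed using a logistic regression, with treatment, age and gender stratification as the main effect", with baseline BMI as a covariate. It lists three contrasts: "The adjusted odds ratios between the top-dose and placebo, between the mid-dose and placebo, and between the top-dose and mid-dose will be calculated together" with 95% confidence intervals. It adds: "The p-values for the comparisons will also be generated". The ≥10% and ≥15% reductions "from baseline in BMI at Week 56 will be analyzed similarly". Protocol 12.5.3 specifies the same model for the two comparisons with placebo.

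SAP 6.1 sets tests as "Two-sided and use a 5% significance level". SAP 6.6.2 applies Hochberg within sets of key secondary variables and makes progress to the next set conditional: "All endpoints have to be statistically significant in favor of top-dose VI-0521 treatment compared to placebo". The process is then repeated for the mid-dose.

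Neither document names the test behind the p-value (Wald, likelihood-ratio or other), a penalised or exact method, the type of confidence limit, or what to do with an empty cell or a non-converging fit. Neither gives an expected responder rate. SAP 6.6.2 does not say how a missing Week 56 responder status is handled, or which endpoints form which set.

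**The concern.** The method that suits a common event at ≥5% is carried over unchanged to a much rarer one at ≥15%, in an arm of 50. When one treatment arm has no events, the likelihood keeps rising as that arm's log-odds falls without limit. There is then no finite maximum-likelihood odds ratio against placebo for either dose, and the promised estimate and upper limit cannot be reported. The Wald standard error grows faster than the coefficient, so the Wald p-value tends to 1 however many active subjects respond.

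A clear benefit could therefore be reported as non-significant with an unusable odds ratio. Choosing a different method after the empty cell is seen would be a data-driven decision on an endpoint under alpha control. A p-value near 1 would also fail its Hochberg set.

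**Working it through.** **Inputs from the documents.** Arms of 50/50/100 with about 30% dropout, giving 35/35/70; difference 2 BMI units; within-treatment SD 2.9 units (SAP 2.3).

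**The plan's own figure.** The only design figure is power for mean BMI change. Power = Φ(δ / [σ√(1/n₁+1/n₂)] − 1.96).
- Mid vs placebo, 35/35: 2/0.693 − 1.96 = 0.925, power 82% (81% with the t distribution; plan: about 80%).
- Top vs placebo, 35/70: 2/0.600 − 1.96 = 1.371, power 91.5% (91.0% with t; plan: at least 90%).

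The stated power reproduces, but it does not bear on the responder endpoints.

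**Step 1: what happens with no placebo responder.** Logistic model with treatment, two binary strata and baseline BMI, fitted to constructed data:

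| Data | ML odds ratio | Wald p | Likelihood-ratio p | Firth odds ratio, p | Fisher p |
|---|---|---|---|---|---|
| Top 30/100 vs 0/50 | about 1e11 | 1.000 | 9e-8 | 45, 7e-7 | 1.5e-6 |
| Mid 10/50 vs 0/50 | about 7e10 | 1.000 | 6e-5 | 30, 3e-4 | 0.001 |
| Top 21/70 vs 0/35 | about 1e11 | 1.000 | 1e-5 | 34, 6e-5 | 7e-5 |

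The finite odds ratios in the ML column only show where the iterations stopped. Stopping after 8 iterations gives Wald p of 0.53 to 0.66 across the scenarios tried. One placebo responder restores the Wald test: top 30% vs 1/50 gives an odds ratio of about 21, p=0.003.

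**Step 2: how likely an empty placebo cell is.** Assumed, because the documents are silent: normal percent change, baseline BMI B of 34 to 40, placebo mean change μ of -2% to +2%. The SD in percentage points is 290/B. Then p = Φ((−15 − μ)/(290/B)) and P(zero) = (1 − p)ⁿ.

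| B | μ | placebo ≥15% rate | P(zero), n=50 | P(zero), n=35 |
|---|---|---|---|---|
| 34 | -2% | 6.4% | 4% | 10% |
| 37 | 0% | 2.8% | 24% | 37% |
| 37 | +2% | 1.5% | 47% | 59% |
| 40 | +2% | 0.95% | 62% | 72% |

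With −10 in place of −15, the same grid gives placebo rates of 17.4% down to 4.9% and P(zero) of about 0% to 8% at n=50 (0% to 17% at n=35). With −5, the lowest placebo rate is Φ(−7/7.25) = 16.7%, so P(zero) is negligible.

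**Step 3: effect on power.** Simulated 50/50/100 trials, top-dose vs placebo:
- True 1.5% vs 25%: Wald 53%, Firth 99%.
- True 2% vs 12%: Wald 11%, Firth 59%.
- The likelihood-ratio test on the planned model kept 69% to 100% power in these scenarios.

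The active rates are assumptions too. At B=37 and μ of 0 to +2%, a difference of 2.0 to 2.4 units moves the mean by 5.4 to 6.5 points and gives about 7% to 14% responders. At such rates Wald power was 0% to 24%, Firth 19% to 65% and likelihood-ratio 44% to 74%.

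**The case against.** The strongest reply is that the SAP never names a Wald test. A reader might infer that the planned p-value will be about 1 whenever placebo is empty. The text does not support that: a likelihood-ratio test fits the same wording and works. This stands for the p-value. It does not rescue the odds ratio or its upper limit, and the SAP does not commit to that test.

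A reader might also infer that an empty placebo arm is the expected outcome. No placebo rate, baseline BMI or SD of percent change is given, and every arm receives the diet and lifestyle programme, which could produce some placebo responders. The range of 4% to 62% is an assumption-based range, not a forecast. The n=35 column is one possibility only: the protocol synopsis treats 30% dropout as a worst case, and Week 56 measurements are sought after treatment discontinuation.

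A third tempting reading is that one failed ≥15% test will halt the top-dose hierarchy. The sets are not listed; if ≥15% sits in the last set, nothing follows it. The block is possible, not certain.

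Imputation might add placebo responders, but SAP 6.6.1 describes it for the primary endpoint, and 6.6.2 gives no rule for responders. Any separated imputed data set would still put a huge standard error into the pooled result.

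**Conclusion.** The concern holds in conditional form. With no placebo responder, the promised odds ratio and upper limit do not exist under maximum likelihood; that part needs no assumption about the test. The near-1 p-value depends on a Wald test, which the SAP neither specifies nor excludes. The chance of the triggering event is about 4% to 62% at n=50 for ≥15%, on the assumptions in Step 2, and at most about 8% for ≥10% on the same grid. No such risk is shown for ≥5%, and top vs mid is unaffected if both arms have responders. The primary analysis is untouched. Since chiefly one threshold of one secondary endpoint is exposed, this is a should-fix point and a cheap improvement, not a flaw that invalidates the plan.

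**What to change.** Before unblinding, state in SAP 6.6.2 that the ≥10% and ≥15% models, and ≥5% for consistency, are fitted by Firth penalised logistic regression with the planned covariates, with p-values and confidence intervals from the penalised profile likelihood. State how responder status is derived when Week 56 is missing and, if multiple imputation is used, how the penalised results are combined. Optionally add a risk difference with an interval that is valid with zero events, such as a score-based interval; a simple Wald interval is not, because its variance is zero in an empty arm.

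The cost is a few SAP sentences and a standard software option. Odds ratios shrink slightly towards 1 when events are plentiful, and power is somewhat below the likelihood-ratio test when the active response is modest (59% against 69% at 2% vs 12%). A smaller alternative is to name the likelihood-ratio test with a penalised or exact fallback on separation, but the odds ratio then comes from a method triggered by the data.
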